A Phase II Trial of Pentoxifylline in Newly-Diagnosed Biliary Atresia

Texas Children's Liver Center, Texas Children's Hospital, Baylor College of Medicine

Principal Investigator:

[name]., Ph.D.
Texas Children's Liver Center (TCLC)
[contact] [name]
E-mail: [contact]

Last approved by the Baylor College of Medicine Institutional Review Board: June 7, 2022
Clinical Trials # NCT01774487

Precis

Biliary atresia (BA) is a devastating liver disease of infancy of unknown etiology, characterized by bile duct obstruction, liver fibrosis, and cirrhosis. BA has no known medical treatments. The only proven treatment is a surgical portoenterostomy (the Kasai procedure, or KP) which can achieve bile drainage and improve outcomes in some cases. The KP's success is variable depending on several factors including age of the infant, experience of the surgeon, and extent of liver fibrosis at the time of KP.

In this study, we conduct a phase II trial of a potential new medical therapy for BA: pentoxifylline (PTX). PTX is a methylxanthine derivative closely related to caffeine that has been used safely in infants with other diseases such as sepsis. In adults, PTX has been shown to have a number of properties beneficial to the liver, including preventing liver fibrosis, improving liver regeneration, and reducing cirrhosis-related complications.

The trial's objective is to determine whether PTX has sufficient biological activity against BA to warrant further study. PTX will be administered orally for 90 days as an adjunct to standard therapy (i.e. KP if appropriate). The primary outcome will measure the change in serum conjugated bilirubin levels after 90 days. Secondary outcomes include changes in body weight, serum markers, liver imaging, and time to liver transplant in infants with BA.

Table of Contents

A. Objectives	4
B. Background and Rationale	4
C. Enrollment Procedures	
i. Inclusion Criteria	4
ii. Exclusion Criteria	5
iii. Pre-treatment Evaluation	5
iv. Patient Registration	5
D. Study Implementation	
i. Study Design	5
ii. Drug Administration	6
iii. Required Observations	6
iv. Dose Modifications	6
v. Concurrent Treatments	6
vi. Removal of Patients from Study	6
E. Data Collection	
i. Clinical Data	6
ii. Adverse Events	6
F. Statistical Considerations	
i. Overview	6
ii. Sample-Size Calculations	7
G. Ethical Issues	8
H. Pharmaceutical Information	8
I. References	10
J. Appendix	
i. Data Safety Monitoring Plan	12
ii. Consent	14

A. Objectives

- 1) To determine whether a 90 day course of oral PTX can improve serum conjugated bilirubin levels in infants with newly-diagnosed BA and receiving standard care
- 2) To describe how PTX therapy affects body weight, serum markers, liver imaging, and time to liver transplantation in infants with BA

B. Background and Rationale

In the US and around the world, biliary atresia (BA) is the most common reason why children require a liver transplant (LT).^{1,2} BA develops early for unknown reasons, appearing in one in 10,000 infants during the first weeks of life. The disease's hallmark feature is bile duct obstruction, which causes bile to back-up and damage the liver. Within months, it progresses to liver fibrosis, cirrhosis, and eventually end-stage liver disease. Hence, without LT, BA becomes incompatible with life.

New therapies that delay or prevent LT are lacking. BA's only therapy – the Kasai portoenterostomy (KP) – was devised in the 1950's in an attempt to restore bile flow.³ The surgery involves removing the obstructed bile ducts and connecting the liver directly to the small intestine. The KP has been shown to improve outcomes in BA. However, its success is variable, depending on a number of factors including age of the child, experience of the surgeon, and extent of pre-existing liver damage.^{4,5} When the KP is unsuccessful, the only remaining treatment is LT.

In this study, we evaluate a novel medical therapy for BA: the methylxanthine derivative pentoxifylline (PTX). PTX has a number of properties that could prevent further liver damage in BA patients. In cell culture PTX inhibits the fibrotic response, and in animal BA models PTX reduces liver fibrosis while promoting weight gain.^{6,7} In humans, PTX improves indices in fatty liver disease, promotes regeneration after liver resection, and reduces morbidity in cirrhotic patients.⁸⁻¹⁰ Importantly, in multiple studies with septic neonates, PTX caused no serious adverse events.¹¹

We hypothesize that PTX will reduce liver damage in patients with BA. To test this, we will compare serum conjugated bilirubin levels (CB) before and after 12 weeks of PTX therapy. Bilirubin levels are an accepted surrogate for cholestasis and liver damage in BA.^{2,4,12} Elevated CB levels reflect two pathological processes: (i) persistent bile back-up from duct blockage, and (ii) impaired bilirubin conjugation from hepatocyte damage. Improving CB levels suggest improving liver function and a better prognosis.^{2,4,5} In our group, 90.4% patients with normal CB levels three months post-KP survived at least two years without needing a LT (n = 21, patients seen between 2006-2010, unpublished data).

We will test PTX using the two-stage “minimax” Phase 2 clinical trial design originally described by Simon.¹³ Phase 2 studies have been most commonly used to determine whether chemotherapeutic agents have sufficient activity to warrant a larger Phase 3 clinical trial. The two-stage “minimax” design identifies therapies with large effects, and has two distinct advantages compared to other designs: (i) early termination if the drug is not efficacious, and (ii) smaller sample sizes without the need for a control arm.

C. Enrollment Procedures

i. Inclusion Criteria (all must be met)

Criteria	Requirement
 Age	0-180 days old
 Diagnosis	Liver biopsy (if inconclusive, intra-operative cholangiogram)

 Prior Therapy  Overall Health  Informed Consent	No previous KP performed at another institution Able to take medications orally Legal guardian signs consent (see Consent in appendix) after understanding risks and investigational nature of study
--	--

ii. Exclusion Criteria

- a) Infants greater than 180 days old
- b) Infants receiving a KP at another institution
- c) Infants unable to take medications orally

iii. Pre-treatment Evaluation

Serum

- Liver panel (including conjugated bilirubin and GGT)
- Complete blood count with differential
- Coagulation profile (PT, PTT, INR)
- Chemistry Panel (including electrolytes and creatinine)
- Pre-albumin
- 25-hydroxy Vitamin D

Imaging

- Complete abdominal ultrasound with Doppler and spleen/liver size measurements

[figure not shown]
Procedures

- KP if deemed eligible by hepatologists and surgeons (Group 1 patients)

iv. Patient Registration – Contact [name] [contact] [name])

D. Study Implementation

i. Study Design

* Measure weight, liver panel, complete blood count, coagulation profile, chemistry, pre-albumin levels

† Measure vitamin D levels, liver size, spleen size

§ Increase PTX according to weight

ii. Drug Administration

- a) Dosage: 20 mg/kg/day divided q 8 hours (i.e., 6.6 mg/kg/dose q 8 hours), in accord with a previous studies in children for other indications¹⁴
- b) Formulation: 20 mg/ml solution made by crushing commercially available PTX 400 mg tablets (Teva Pharmaceuticals USA, Sellersville, PA) and diluting per established recipe written by Nahata MC, Pediatric Drug Formulation, 5th Edition, pg. 215.

iii. Required Observations

	Week 2	Week 4	Week 8	Week 12
Weight				
Liver panel				
Complete Blood Count				
Coagulation Profile				
Chemistry Panel				
Pre-Albumin				
25-OH Vitamin D				
Liver Ultrasound				
Adjust PTX dose				

iv. Dose Modifications – Increase according to weight at clinic visits 2, 4, and 8 weeks after starting PTX

v. Concurrent Treatments

- a) Standard therapies: All standard therapies will be given during PTX therapy, including ursodiol, fat-soluble vitamins, and post-KP antibiotics
- b) Experimental therapies: No other experimental therapies will be given during PTX therapy

vi. Removal of Patients from Study

- a) Non-medical reasons: Parents may voluntarily exclude their infant from the study at any time; in addition, patients may be removed from the study if they are not compliant with taking PTX as prescribed
- b) Medical reasons: In the event of a serious adverse event, the study team and the IRB will determine whether the patient should be removed from the study (see Data Safety Monitoring Plan in appendix)

E. Data Collection

- i) **Clinical Data** – All clinical data (weights, laboratory results, imaging results) will be stored in the patient's electronic medical record
- ii) **Adverse Events** – All adverse events reported by parents or noted by physicians will be recorded in the patient's medical record. They will also be reported to the IRB following a pre-determined schedule (see Data Safety Monitoring Plan in appendix)

F. Statistical Considerations

- i) **Overview**

This is a Phase 2 clinical trial using the two-stage "minimax" design described by Simon.¹³ As a Phase 2 trial, the trial's objective is to determine whether PTX has sufficient biological activity against BA to warrant further study. By choosing the two-stage "minimax" design, we gain two advantages: (i) early termination if the drug is not efficacious, and (ii) an overall smaller sample size to test the hypothesis. One limitation is that the design identifies only large effects (response >20%). For BA this is appropriate, because the field is in need of a robust therapy that can substantially limit liver damage and delay/prevent need for LT.

The Phase 2 design involves administering PTX to all subjects and comparing their response to historical controls. Hence, the study has no randomization or control arm. Historical controls from BA patients seen at Texas Children's hospital between 2006-2010 will be used. Of those receiving the KP (equivalent to Group 1 study subjects), 21/36 or 58.3% had normal CB levels 3 months post-KP. This agrees with previously published figures from other centers.¹⁵ Of those not receiving the KP (equivalent to Group 2 study subjects), 1/13 or 7.7% had stable CB levels after 3 months.

Historical controls in this study are appropriate for a number of reasons. The same two pediatric surgeons performing all of the KPs in the past will perform the KPs for future study subjects. Furthermore, neither the KP surgical technique nor our medical management of patients with BA has changed over the years. Rather, the only difference is that the number of patients with BA seen at Texas Children's Hospital has increased. One potential bias that may arise is that we may be more vigilant to ensure study subjects take PTX, which may lead to more overall care. To control for this, we will adhere to the same clinic schedule and guidelines as we have used in the past.

In this study, Group 1 and Group 2 patients will be analyzed independently:

[figure not shown]
- Group 1) Infants receiving the KP will be given PTX for 12 weeks, and the number whose CB levels return to normal (0.0-0.3 mg/dL) will be calculated. Historically, as mentioned above, ~60% of such infants have normal CB levels after 12 weeks. The study will determine whether PTX improves this percentage.
- Group 2) Infants not receiving the KP will be given PTX for 12 weeks, and the number whose CB levels stabilize (within 10% of starting level) will be calculated. Historically, as mentioned above, ~10% of such infants have stable CB levels after 12 weeks. The study will determine whether PTX improves this percentage.

ii) Sample-Size Calculations

For sample size calculations, we use previously-derived tables for the "minimax" design for two-stage studies described by Simon.¹³ Because BA is in need of a robust therapy, we designed the study to detect a large effect (>20% increase in responders). We used standard values for significance (alpha = 0.05) and power (beta = 0.2). Our total sample size is the sum of patients needed in Groups 1 and 2 (35 and 25, respectively).

For Group 1, approximately 60% of patients receiving the KP have a normal CB (0.0-0.3 mg/dL) 12 weeks later based on historical data (null hypothesis). We are interested in determining whether PTX can increase this to 80% of patients (alternative hypothesis), which would be a large enough response to make the medication worth pursuing in a larger Phase 3 trial. To test the null hypothesis versus the alternative hypothesis at a significance level of 0.05 and power of 80%, 35 patients must be enrolled. Of these 35, 26 or more patients must respond to reject the null hypothesis. Furthermore, the study will be terminated early if, of the first 13 patients, fewer than 9 respond.

For Group 2, approximately 10% of patients not receiving a KP have a stable CB (within 10% of the starting CB) 12 weeks after diagnosis based on historical data (null hypothesis). We are interested in determining whether PTX can increase this to 30% of patients (alternative hypothesis), which would be a large enough response to make the medication worth pursuing in a larger Phase 3 trial. To test the null hypothesis versus the alternative hypothesis at a significance level of 0.05 and power of 80%, 25 patients must be enrolled. Of these 25, 6 or more patients must respond to reject the null hypothesis. Furthermore, the study will be terminated early if, of the first 15 patients, fewer than 2 respond.

G. Ethical Issues

i) Informed consent

Participants will only be enrolled after their parents understand the nature and objectives of the trial, as well as the attendant risks and possible discomforts. All families will be given a consent form describing PTX and possible side-effects (see Consent in appendix).

ii) Children as research subjects

PTX may benefit patients with BA by reducing progression of the disease. This study does have risks. PTX has been studied extensively in pediatric populations and is commonly associated with emesis. However, it has never been found to cause any serious adverse events in children. This study also involves blood draws. However, these blood draws are part of routine clinical care, and would be performed independent of participation in this trial.

H. Pharmaceutical Information

- i) **Formulation** – 20 mg/ml compounded from 400 mg tablets by Texas Children's Hospital Pharmacy
- ii) **Storage** – Store opened bottles at 4°C for 1 month

iii) Administration – Orally with needleless syringe in sides of mouth**iv) Toxicities**

PTX is a methylxanthine derivative, belonging to the same family of molecules as caffeine. It has been widely studied in septic neonates as well as adults with liver disease, and no serious adverse effects have been reported. In the neonatal studies, PTX was well-tolerated and no patients were withdrawn because of side-effects.¹¹

The PTX side-effect profile also has been reported in children ages 6 months to 5 years taking 20 mg/kg/day orally for Kawasaki disease.¹⁴ Fifteen of 24 patients reported mild to moderate adverse events that may or may not have been related to PTX, and none had to discontinue the medication. The adverse events included vomiting/spitting out immediately after dosing (11 episodes in 7 patients) and abdominal pain (6 episodes in 3 patients). Eight patients reported 14 non-gastrointestinal events, including mild cough, inability to walk without help, I/VI systolic flow murmur anemia, clear rhinorrhea, diaper rash, irritability, and temporary hearing loss. No dose-limiting, unusual, or idiosyncratic reactions were observed in this study.

In addition, in adult studies, PTX does lead to vomiting and epigastric discomfort in less than 1% of patients. These symptoms were reversed when the medication was stopped.⁸ In adults, PTX was also trialed peri-operatively with no excess serious side-effects compared to controls.⁹ A summary of the side-effect profile is as follows:

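### Section D.vi removes infants from the study after PTX starts, but Section F does not say how they count toward 26 of 35; would-be responders whose week-12 CB goes unused take Group 1 below its stated 80% power

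*Combined protocol and SAP*

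**What the plan says.** - **Removal (D.vi).** Three routes lead out of the study itself, not merely off PTX. Parents: "Parents may voluntarily exclude their infant from the study at any time". Non-compliance: "patients may be removed from the study if they are not compliant with taking PTX as prescribed". After a serious adverse event, the study team and the IRB decide.
- **Response (F.i).** For Group 1, "the number whose CB levels return to normal (0.0-0.3 mg/dL) will be calculated" after 12 weeks. The definition does not mention death, transplant, removal or a missing value.
- **Decision rule (F.ii).** "Of these 35, 26 or more patients must respond to reject the null hypothesis", and "the study will be terminated early if, of the first 13 patients, fewer than 9 respond". The total sample size is 35 plus 25, with no inflation for dropout and no replacement rule.
- **Setting.** The trial is single-arm (F.i: "the study has no randomization or control arm"). The liver panel is taken at weeks 2, 4, 8 and 12 (D.iii).
- **Data likely to exist.** Section G.ii describes the blood draws as routine care that would happen without the trial. Section E says of the results: "All clinical data (weights, laboratory results, imaging results) will be stored" in the electronic medical record.
- **Withdrawals elsewhere.** The Data Safety Monitoring Plan requires withdrawals to be reported to the IRB within 7 days. It does not say how they enter the analysis.

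**The concern.** The primary decision rests on a count, and the plan does not say what a removed infant contributes to it. The wording in F.ii suggests that the infant stays in the denominator. It does not say whether that infant's week-12 CB, which will usually still be drawn in routine care, may count in the numerator. Two analysts could follow the text and reach different totals, and the choice could be made after responses are known.

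The stake is mainly power. The design exceeds 80% by less than one percentage point, and a fixed threshold of 26 cannot absorb the loss of infants who would have responded. An active treatment could be dropped because results sitting in the chart were not used.

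A second gap lies in the same definition. Group 1 response depends on CB alone, so nothing in F excludes a normal CB obtained after liver transplant. Section F.i gives delaying or preventing transplant as part of the reason for seeking a therapy, and time to transplant is a secondary outcome.

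**Working it through.** **Inputs (F.ii).** Null rate 0.60, alternative 0.80, alpha 0.05, power 0.80. Stage 1 has 13 infants and continues with 9 or more responders. The total is 35, and 26 or more responders reject the null.

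**Formula.** With b the binomial probability, n1 the stage 1 CBs and n the total CBs:

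P(reject) = Σ over x from 9 to n1 of b(x; n1, p) × P(Bin(n − n1, p) ≥ 26 − x)

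**1. The plan's own figure** (n1 = 13, n = 35, p = 0.80):

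| x | b(x; 13, 0.8) | P(Bin(22, 0.8) ≥ 26 − x) | product |
|---|---|---|---|
| 9 | 0.1535 | 0.7326 | 0.1125 |
| 10 | 0.2457 | 0.8670 | 0.2130 |
| 11 | 0.2680 | 0.9439 | 0.2530 |
| 12 | 0.1787 | 0.9799 | 0.1751 |
| 13 | 0.0550 | 0.9939 | 0.0546 |

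The sum is 0.808. The same formula at p = 0.60 gives type I error 0.0499. The stated design is reproduced.

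**2. CBs unused for reasons unrelated to response, no replacement, cut-offs 9 and 26 kept.** The numbers lost are assumptions; the plan gives none.

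| CBs unused | n1 | n | Power (p = 0.80) | Type I error (p = 0.60) |
|---|---|---|---|---|
| None | 13 | 35 | 0.808 | 0.050 |
| One, after stage 1 | 13 | 34 | 0.743 | 0.031 |
| Two, after stage 1 | 13 | 33 | 0.650 | 0.018 |
| One, among the first 13 | 12 | 34 | 0.681 | 0.026 |

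In the last row the chance of stopping wrongly at stage 1, P(X ≤ 8) at p = 0.80, rises from 0.099 with 13 CBs to 0.205 with 12.

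**3. The same loss as a rate.** If a fraction m is missing independently of outcome and counted as non-response, the response rate becomes p(1 − m). At an assumed m = 5% (35 × 0.05 = 1.75 infants on average), the alternative becomes 0.80 × 0.95 = 0.76 and power is 0.626. The null becomes 0.60 × 0.95 = 0.57 and type I error is 0.023.

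**4. Removed infants who would all have been non-responders.** They add nothing to the count whether or not their CBs are used. With none replaced, the operating characteristics stay at 0.050 and 0.808.

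**5. Dependence on the stage 1 wording.** Stopping Rule 1 in the Data Safety Monitoring Plan stops Group 1 when 9 of the first 13 do not respond, that is, with 4 or fewer responders. F.ii stops with 8 or fewer. Read literally, the appendix rule almost never stops at p = 0.80 (probability 0.0002). Power is then 0.854 with complete CBs and 0.773 with one lost. The stage 1 figures above hold only under F.ii.

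**6. Group 2** (at least 2 of 15, then 6 of 25; 0.10 against 0.30). Power is 0.802 with complete CBs and 0.768 with one lost after stage 1.

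**The case against.** The best defence is that F.ii already fixes the denominator. Thirty-five are enrolled and 26 of those must respond, so an unobserved infant simply fails to respond, the test becomes conservative, and a phase II screen can tolerate that. Because the draws are routine and the results are kept, few CBs may be missing at all. Study design figures and some later pages were also not available for review.

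Much of this stands. The denominator reading is the natural one, and on it type I error goes down. Actual attrition is unknown. But the same facts sharpen the remaining question: if the CB will usually exist, the plan must say whether the CB of an infant removed under D.vi counts. It does not, and power is what suffers if the answer is no.

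Three stronger readings are tempting and are not supported.

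- *A reader might infer that removing poor responders inflates type I error.* That needs removed infants to be replaced, and no available passage provides for replacement.
- *A reader might infer that removals would be steered by the CB trend.* The schedule ("Measure weight, liver panel, complete blood count, coagulation profile, chemistry, pre-albumin levels") makes the trend visible in an unblinded trial, but the text on non-compliance names no decider and nothing shows that CB would guide removal.
- *A reader might infer that the plan counts a transplanted infant as a PTX success.* No sentence says so. F only fails to exclude it, and the documents do not show whether any infant is transplanted within 12 weeks.

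**Conclusion.** The point holds in limited form. D.vi takes infants out of the study, F.ii counts responders against fixed thresholds with no allowance for loss, and nothing available connects the two. The 80.8% power is therefore conditional on complete week-12 CBs. A single unused CB brings it to 74.3% after stage 1, or to 68.1% among the first 13 under F's rule.

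These figures assume that the loss is unrelated to response, that no infant is replaced and that the cut-offs stay as written. Losses confined to would-be non-responders cost nothing. The type I error is not shown to be at risk. The transplant gap is one of definition, with a size that cannot be derived from the documents. The matter should be settled before responses are analysed, but it does not invalidate the design, and it does not by itself call for a larger sample.

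**What to change.** **Section D.vi.** State that stopping PTX or non-compliance is not removal from the analysis, and that the routine week-12 CB is used unless consent for follow-up is withdrawn. This changes how infants are counted, not any clinical decision about PTX.

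**Section F.**
- Analyse every infant who starts PTX. Tie the totals of 35 and 25 and the stage 1 counts of 13 and 15 to that set, without replacement.
- Require the group's CB criterion at week 12 with the native liver. Count death, transplant or a truly missing CB as non-response, with a sensitivity analysis in infants who have an evaluable week-12 CB.
- Apply the same rule to the 36 and 13 historical infants, and report their deaths, transplants and missing CBs. The text does not say how these were counted.
- State that the 80.8% power for Group 1 requires complete week-12 CBs, and that it is about 63% at an assumed 5% missing independently of outcome.
- Reconcile the stage 1 rule in F.ii with Stopping Rule 1 in the Data Safety Monitoring Plan.

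**Cost.** A few sentences, and a chart check of 36 + 13 = 49 historical infants. The drawback is a less favourable stated power if CBs are missing: counting them as non-response makes the loss explicit but does not recover it. Obtaining the routine CBs does.

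### Group 2 response is a band of 10% around the starting CB with no direction, so read as written an infant whose CB falls by more than 10% counts as a failure

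*Combined protocol and SAP*

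**What the plan says.** Section F.i (Overview) defines the Group 2 outcome at 12 weeks: "the number whose CB levels stabilize (within 10% of starting level) will be calculated". Section F.ii (Sample-Size Calculations) uses the same band for the historical rate, as the share of infants who "have a stable CB (within 10% of the starting CB) 12 weeks after diagnosis". Neither wording says whether the band is two-sided or only an upper limit.

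Two decisions in F.ii rest on this definition. The study stops early if, "of the first 15 patients, fewer than 2 respond". At the end, "Of these 25, 6 or more patients must respond to reject the null hypothesis". The null rate of 10% comes from the historical series in F.i, where "1/13 or 7.7% had stable CB levels after 3 months"; the direction used in that count is not given either. The stopping rules in the Data Safety Monitoring Plan speak of response without defining it.

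Other sections set the direction of benefit. Objective 1 asks whether pentoxifylline "can improve serum conjugated bilirubin levels in infants with newly-diagnosed BA". Section B states: "Improving CB levels suggest improving liver function and a better prognosis". Section G.ii states: "PTX may benefit patients with BA by reducing progression of the disease".

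**The concern.** In ordinary use, within 10% of the starting level means between 90% and 110% of it. An infant whose CB falls by 40% lies outside that band. The rule as written scores this infant as a failure, in the same category as one whose CB has risen by 40%. That contradicts Objective 1 and section B, both of which treat lower CB as the favourable result. The Group 1 endpoint, return of CB to the normal range, does not have this problem.

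The verb used for Group 2 and the aim of slowing progression in G.ii suggest that the authors wanted to count every infant whose CB does not worsen. If so, the text does not say it. In a single-arm trial judged against a fixed historical rate, an open reading of response could be settled after the results are seen, and one infant can decide the outcome.

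**Working it through.** **Inputs.** From F.ii, Group 2: null rate 10%, alternative 30%, alpha 0.05, power 80%; 15 infants at the look, with at least 2 responders needed to continue; 25 in all, with at least 6 responders needed to reject. From F.i: historical count 1/13 = 7.7%. Not in the documents: the share of infants whose CB falls by more than 10%. That share is assumed below and a range is shown.

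**Step 1: reproduce the plan's design.** With response probability p,

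P(reject) = Σ (x = 2 to 15) Bin(x; 15, p) × P[Bin(10, p) ≥ 6 − x].

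- p = 0.10: P(reject) = 0.0328 (type I error); probability of stopping at the look 0.549.
- p = 0.30: P(reject) = 0.8017 (power); probability of stopping at the look 0.035.

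A search for the minimax design at these rates and error limits returns the same rule. The sample size and cut-offs are therefore correct for whatever event is called response. The open question is which event that is.

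**Step 2: an example at the cut-off.** Of 25 infants, 6 do not worsen, and one of these 6 falls by more than 10%. As written, the count is 5/25 and the null stands. With falls counted, it is 6/25 and the null is rejected. This shows that the decision can flip, not that a flip is likely.

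**Step 3: size of the loss.** Let q be the share of infants whose CB does not rise by more than 10%, and s the fraction of these whose CB falls by more than 10%. The rate inside the band is then q(1 − s). For example, q = 0.30 and s = 0.10 give 0.30 × 0.90 = 0.270. Putting that rate into the Step 1 formula:

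| q | s (assumed) | Rate in band | Power as written | Power if falls count |
|---|---|---|---|---|
| 0.30 | 2% | 0.294 | 0.78 | 0.80 |
| 0.30 | 5% | 0.285 | 0.75 | 0.80 |
| 0.30 | 10% | 0.270 | 0.70 | 0.80 |
| 0.30 | 25% | 0.225 | 0.50 | 0.80 |
| 0.30 | 50% | 0.150 | 0.16 | 0.80 |
| 0.40 | 5% | 0.380 | 0.95 | 0.97 |
| 0.40 | 10% | 0.360 | 0.93 | 0.97 |
| 0.40 | 25% | 0.300 | 0.80 | 0.97 |
| 0.40 | 50% | 0.200 | 0.38 | 0.97 |

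At q = 0.30, the probability of stopping at the look rises from 0.035 (s = 0) to 0.058, 0.117 and 0.319 at s = 10%, 25% and 50%.

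Every infant inside the band is also one who did not worsen, so a rejection under the written rule is always a rejection when falls count. The probability that the two readings disagree is therefore the difference between the two power columns. At q = 0.30 it is 0.02, 0.05, 0.10, 0.30 and 0.64 down the table. It restates the power loss and is not a second effect.

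**Step 4: the historical rate.** Counting falls as response in the trial requires the same for the 13 historical infants. If the count stays 1/13, the 10% null stands. If one more infant qualifies, the rate is 2/13 = 15.4%, and a 20-point gain means 35.4%. Keeping the look at 2 of 15:

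| Cut-off | Type I error at 15.4% | Power at 30% | Power at 35.4% |
|---|---|---|---|
| 6/25 | 0.17 | 0.80 | 0.92 |
| 7/25 | 0.077 | 0.66 | 0.84 |
| 8/25 | 0.029 | 0.49 | 0.71 |

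**The case against.** The strongest reply is that this is a missing phrase and not an error of design. The objectives, the rationale and the word used for Group 2 all point towards counting infants who do not worsen, and a team working to those aims would hardly score a large fall as a failure. The direction might also appear in the figures that are not reproduced in the available copy, one of which stands directly before the Group 2 definition. Both points are fair. They bear on intent and on what could be seen; the only numerical criterion in the available text, given twice, is still an undirected band.

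Secondly, F.ii sets 30% as the rate under the stated definition. If that means 30% inside the band, power is 0.80 as planned, and the losses in Step 3 appear only when the 30% is assigned to infants who do not worsen. This is correct, so the table describes the cost of a mismatch and not a deficit in the planned design.

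Thirdly, the worst rows need many large falls in infants without surgery, whose disease section B describes as progressive. At q = 0.30, the expected number of infants lost among 25 is 25 × 0.30 × s: about 0.4 at s = 5%, 0.75 at 10%, 1.9 at 25% and 3.8 at 50%. Nothing in the documents supports the higher shares. Nothing excludes them either, since F.i does not say how CB moved in the other 12 historical infants and an active drug would be expected to produce falls.

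Finally, F.ii applies the same band to the historical rate, so if trial and history are scored alike the type I error holds. That stands, and it is why the recount belongs in the fix.

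**Conclusion.** The concern holds. Applied as written, the Group 2 rule counts a CB fall of more than 10% as non-response at both decision points, against the trial's own objective. The stated design is arithmetically sound.

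The gap in the text is certain; its effect is not. With 30% of infants not worsening, power drops by 0.02 to 0.10 if 2% to 10% of them have large falls. It drops to 0.50 or 0.16 only if a quarter or a half do. These shares are assumptions. If large falls are rare, the two readings nearly coincide. That the authors meant CB that does not worsen is an inference from the surrounding text. The point should be fixed because one infant can change the decision and the correction is cheap.

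**What to change.** In both places in section F where the band appears, define Group 2 response as week-12 CB no higher than 110% of the starting CB, with any fall counted as response. Before any analysis, including the 15-infant look, recount the 13 historical infants under the same rule and state the result.

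- If the count is still 1/13, nothing else changes.
- If it rises, restate the null rate and the type I error and power that 25 infants deliver.

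The cost is one line of definition in two places and a re-read of 13 existing charts; the 25 infants remain. The downside is that a higher recount makes the operating characteristics less favourable. At 2/13 with the present look, 7/25 exceeds the 0.05 limit and 8/25 falls short of 80% power even for a 20-point gain. The plan would then have to state which departure it accepts; holding both targets would need a different design.
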